All adverse events that occur after the consent form is signed but before treatment allocation/randomization must be reported by the investigator if they cause the subject to be excluded from the trial, or are the result of a protocol-specified intervention, including but not limited to washout or discontinuation of usual therapy, diet, placebo treatment or a procedure. From the time of treatment allocation/randomization through 30 days following cessation of treatment, all adverse events must be reported by the investigator. Such events will be recorded at each examination on the Adverse Event case report forms/worksheets. The reporting timeframe for adverse events meeting any serious criteria is described in Section 7.2.3.1. The investigator will make every attempt to follow all subjects with non-serious adverse events for outcome.

Electronic reporting procedures can be found in the Electronic Data Capture (EDC) data entry guidelines. Paper reporting procedures can be found in the Investigator Trial File Binder (or equivalent).

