### **7.2.3 Immediate Reporting of Adverse Events to the Sponsor**

#### **7.2.3.1 Serious Adverse Events**

An SAE is any AE occurring at any dose or during any use of Sponsor's product that:

- Results in death;
- Is life-threatening;
- Results in persistent or significant disability/incapacity;
- Results in or prolongs an existing inpatient hospitalization;
- Is a congenital anomaly/birth defect;
- Is another important medical event.

\*Note: In addition to the above criteria, AEs meeting either of the below criteria, although not serious per ICH definition, are reportable to the Sponsor in the same timeframe as SAEs to meet certain local requirements. Therefore, these events are considered serious by the Sponsor for collection purposes.

- Is a new cancer (that is not a condition of the study);
- Is associated with an overdose.

Refer to [Table 10](#) for additional details regarding each of the above criteria.

For the time period beginning when the consent form is signed until treatment allocation/randomization, any SAE, or follow up to an SAE, including death due to any cause other than progression of the cancer under study (see Section 7.2.3.3 for additional details), that occurs to any subject must be reported within 24 hours to the Sponsor if it causes the subject to be excluded from the trial, or is the result of a protocol-specified intervention, including but not limited to washout or discontinuation of usual therapy, diet, placebo treatment or a procedure.

For the time period beginning at treatment allocation/randomization through 90 days following cessation of trial treatment, or 30 days following cessation of trial treatment if the subject initiates new anticancer therapy, whichever is earlier, any SAE, or follow up to a SAE, including death due to any cause other than progression of the cancer under study (see Section 7.2.3.3 for additional details), whether or not related to the Sponsor's product, must be reported within 24 hours to the Sponsor either by electronic media or paper. Electronic

reporting procedures can be found in the EDC data entry guidelines. Paper reporting procedures can be found in the Investigator Trial File Binder (or equivalent).

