### 8.6.1.2 Overall Survival

The non-parametric Kaplan-Meier method will be used to estimate the survival curves. The treatment difference in survival will be assessed by the stratified log-rank test (based on the stratification factor defined in Section 5.4). A stratified Cox proportional hazard model with Efron's method of tie handling will be used to assess the magnitude of the treatment difference (ie, the HR). The HR and its 95% CI from the stratified Cox model with a single treatment covariate will be reported. The stratification factors used for randomization (See Section 5.4) will be applied to both the stratified log-rank test and the stratified Cox model. Restricted Mean Survival Time (RMST) method may be conducted for OS to account for the possible non-proportional hazards effect.

Since subjects in the placebo+EP arm are expected to discontinue from the study earlier compared to subjects in the pembrolizumab arm because of earlier onset of PD and may switch to another anti PD-1 treatment following confirmation of PD, adjustment for the effect of crossover on OS may be performed based on recognized methods, (eg, the Rank Preserving Structural Failure Time (RPSFT) model proposed by Robins and Tsiatis [115]), based on an examination of the appropriateness of the data to the assumptions required by the method used.

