The threshold of at least 10% was chosen for membership in Tier 2 because subjects enrolled in this study are in critical condition and usually experience various AEs of similar types regardless of treatment, events reported less frequently than in 10% of subjects would obscure the assessment of the overall safety profile and add little to the interpretation of potentially meaningful treatment differences. In addition, Grades 3 to 5 AEs ( $\geq 5\%$  of subjects in one of the treatment arms) and SAEs ( $\geq 5\%$  of subjects in one of the treatment arms) will be considered Tier 2 events. For Tier 2 events, 95% CIs will be provided for between-treatment differences in the percentage of subjects with events; these analyses will be performed using the Miettinen and Nurminen method [116], an unconditional, asymptotic method. Because many 95% CIs may be provided without adjustment for multiplicity, the CIs should be regarded as a helpful descriptive measure to be used in safety review, not a formal method for assessing the statistical significance of the between-treatment differences.

For laboratory parameters, the number and percentage of subjects with increases from baseline in laboratory test toxicity grades based on the highest post-baseline toxicity grade and shift of toxicity grade from baseline to the worst post-baseline toxicity grade will be summarized by treatment arm.

Table 14 Analysis Strategy for Safety Parameters

Safety Tier	Safety Endpoint	95% CI for Treatment Comparison	Descriptive Statistics
Tier 2	Any AE ( $\geq 10\%$ of subjects in one of the treatment arms)	X	X
	Any Grades 3 to 5 AE ( $\geq 5\%$ of subjects in one of the treatment arms)	X	X
	Any serious AE ( $\geq 5\%$ of subjects in one of the treatment arms)	X	X
Tier 3	Any AE		X
	Any change from baseline results (laboratory tests)		X

Abbreviations: AE=adverse event, CI=confidence interval

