## 8.9 Sample Size and Power Calculations

Four hundred and thirty subjects were planned to be randomized in 1:1 ratio into pembrolizumab+EP and the saline placebo+EP arms. By the time of the current amendment, 453 subjects were enrolled for this study.

The final PFS analysis for the study will occur about 22 months from study start. If 387 PFS events occur by the time of the final PFS analysis, the study will have a power of 96% approximately to demonstrate a HR of 0.65 on PFS at initially allocated  $\alpha=0.006$ .

The final OS analysis will occur when at least 294 events have occurred or approximately 31 months from study start, whichever occurs later. With a minimum of 294 events at the time of final analysis, the study has at least 94% power to demonstrate a HR of 0.65 on OS at initially allocated  $\alpha=0.019$ .

The above power calculations for OS and PFS are based on the following assumptions: 1) 453 subjects were enrolled over 14.5 months following the actual enrollment pattern; 2) median PFS is 4.3 months in the control arm and HR is 0.65; 3) median OS is 10 months in the control arm and HR is 0.65; 4) The exponential dropout rates assumed for OS and PFS are 1% per month.

The sample size and power calculations were performed in the software R (package “gsDesign”).

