## **Exposure-Adjusted Approach**

To properly account for the potential difference in follow-up time between the study arms, which is expected to be longer in the pembrolizumab arm, summary of AE incidence adjusted for treatment exposure analyses may be provided as appropriate.

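### Tier 2 adverse event CIs compare crude percentages over a window tied to the end of treatment, which the plan expects to last longer on pembrolizumab, and the exposure adjustment is only optional

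*Combined protocol and SAP*

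**What the plan says.** Protocol 8.6.2 and sSAP 3.5.2 name no Tier 1 safety events. Between-arm safety comparisons are made for Tier 2: "For Tier 2 events, 95% CIs will be provided for between-treatment differences in the percentage of subjects with events", by the Miettinen and Nurminen method. Table 14 of the protocol lists three Tier 2 rows: any AE, Grade 3 to 5 AEs, and serious AEs. The same section adds that "the CIs should be regarded as a helpful descriptive measure to be used in safety review" and that they are not a formal significance method.

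The collection windows follow treatment. Protocol 7.2: "From the time of treatment allocation/randomization through 30 days following cessation of treatment, all adverse events must be reported by the investigator". For SAEs, 7.2.3.1 has a longer tail: "For the time period beginning at treatment allocation/randomization through 90 days following cessation of trial treatment", cut to 30 days if new anticancer therapy starts, whichever is earlier.

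The plan expects the arms to differ. Protocol 8.6.1.2 says of control subjects: "placebo+EP arm are expected to discontinue from the study earlier compared to subjects in the pembrolizumab arm because of earlier onset of PD". The sSAP, under Exposure-Adjusted Approach, refers to the "potential difference in follow-up time between the study arms, which is expected to be longer in the pembrolizumab arm". Its response is that a "summary of AE incidence adjusted for treatment exposure analyses may be provided as appropriate". It gives no method, denominator, trigger or interval. Protocol 8.6.2 has no such provision, and 8.12 only summarises the number of cycles received.

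**The concern.** A percentage of subjects with an event depends on both how often the event occurs and how long each subject is watched. Here the watching ends soon after treatment ends, and pembrolizumab or placebo continues up to 35 cycles unless a discontinuation criterion such as progression comes first. If pembrolizumab delays progression, its subjects are observed for longer. For an event that accrues steadily on treatment, the crude difference then mixes any real increase in rate with extra observation time, and the second part grows with the PFS benefit the trial hopes to show.

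At stake is how the safety tables are read. The plan names the problem and the direction, yet leaves open whether and how to adjust, so that choice could be made after unblinded results are seen.

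**Working it through.** **Inputs from the documents.** "median PFS is 4.3 months in the control arm and HR is 0.65" (protocol 8.9); 35 cycles of 3 weeks; a 30-day tail for AEs and up to 90 days for SAEs; 453 subjects randomized 1:1, taken as 227 and 226, all treated.

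**The plan's own figure.** No figure is stated for the AE comparison. The figure that uses the same HR is PFS power, stated as 95.6% for 387 events at one-sided 0.006.
- Fixed design: Φ(√387/2 × |ln 0.65| − 2.512) = Φ(4.237 − 2.512) = 95.8%.
- With the two planned looks (332 and 387 events, Lan-DeMets O'Brien-Fleming spending): 95.5%, with 0.0030 spent at IA1 and a final nominal level of 0.0051, as in Table 15.

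The stated figure reproduces.

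**Assumptions.** The documents give no expected exposure. Treatment time is taken as exponential with the PFS medians, 4.3 months and 4.3/0.65 = 6.6 months. It is capped at c = 35 × 21/30.44 = 24.15 months and followed by a tail w = 30/30.44 = 0.986 months. The event hazard λ is constant and identical in both arms. Dropout, treatment past progression and data cutoff are ignored at first.

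**Formulas.** With treatment-stopping hazard h (0.1612 control; 0.1612 × 0.65 = 0.1048 pembrolizumab):
- Mean window = (1 − e^(−hc))/h + w
- P(event) = 1 − e^(−λw) × [h/(h+λ) × (1 − e^(−(h+λ)c)) + e^(−(h+λ)c)]

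**Mean window.** 7.1 months control, 9.8 months pembrolizumab.

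**Worked case, λ = 0.05 per month.**
- Control: 1 − 0.9519 × (0.7633 × 0.9939 + 0.0061) = 27.2%
- Pembrolizumab: 1 − 0.9519 × (0.6770 × 0.9762 + 0.0238) = 34.8%

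**All four hazards, HR 0.65, 30-day tail.** The last column is the probability that the Miettinen-Nurminen 95% CI lies wholly above zero; it is 2.5% when windows are equal.

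| λ per month | Control | Pembrolizumab | Difference | CI above 0 |
|---|---|---|---|---|
| 0.02 | 12.6% | 16.9% | +4.3 | 25% |
| 0.03 | 18.0% | 23.7% | +5.7 | 32% |
| 0.05 | 27.2% | 34.8% | +7.6 | 42% |
| 0.08 | 38.1% | 47.1% | +9.0 | 49% |

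**Sensitivity, same four hazards.**

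| Scenario | Difference, points | CI above 0 |
|---|---|---|
| HR 0.65, cutoff at 22 months, uniform 14.5-month accrual assumed | +2.8 to +7.0 | 14% to 33% |
| HR 0.75 | +2.8 to +6.0 | 13% to 25% |
| HR 0.85 | +1.5 to +3.3 | 7% to 11% |
| HR 1.0 | 0 | 2.5% |

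**SAEs.** With the full 90-day tail at HR 0.65 the mean windows are 9.0 and 11.7 months. At control percentages of 5%, 10% and 20% the excess is +1.4, +2.7 and +4.9 points, and the CI lies above zero in 10%, 14% and 24% of trials. With the 30-day tail at the same percentages the figures are +1.8, +3.5 and +6.2 points, and 13%, 21% and 34%.

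**Events confined to the first 84 days** (four undelayed cycles). Control percentages of 10%, 30% and 50% become 10.3%, 30.8% and 51.2%, so the crude excess is +0.3 to +1.2 points.

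**What a person-time rate does.**
- Constant hazard, λ = 0.05: expected person-time to first event or window end is 0.2721/0.05 = 5.44 months control and 0.3483/0.05 = 6.97 months pembrolizumab. Both arms then give 5.0 first events per 100 person-months.
- Events confined to 84 days: dividing by the total window gives, at 30%, (0.308/9.77)/(0.300/7.06) = 0.74. Stopping person-time at the first event gives 0.75 to 0.77 across the three percentages. Either way the rate falsely favours pembrolizumab.

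**The case against.** The strongest reply has four parts.

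- **The CIs are descriptive.** This stands. No test, alpha or stopping rule rests on them, so a reader who infers inflated type I error or a faulty safety decision rule goes beyond the text. But the disclaimer addresses multiplicity. It does not warn of a shift in a known direction.
- **The sSAP already covers it.** In part. It names the issue, but it permits an analysis without committing to or defining one.
- **Crude incidence is a legitimate quantity.** It is: it describes the burden over the regimen as given. It cannot separate a higher rate from longer observation, so it should be kept and supplemented.
- **The size rests on an assumed exposure.** This also stands. Treatment also stops for toxicity, may continue past progression in both arms, and is cut by the data cutoff; each breaks the equation of treatment time with PFS.

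Two stronger readings are tempting. One is that every Tier 2 interval rests on a 30-day window; the SAE row does not. The other is that an event with equal rates will be shown as excess harm; even in the least favourable case in the main table, about half of trials would show no CI above zero.

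**Conclusion.** The concern holds in a limited form. For events that accrue throughout treatment, the planned crude comparison leans towards more events on pembrolizumab whenever that arm is treated longer, which the plan itself expects. Under the PFS-based assumption at HR 0.65 the lean is about 4 to 9 percentage points, large enough for a one-sided signal in a quarter to a half of trials. It shrinks with earlier cutoff or a smaller PFS effect, is smaller for SAEs, is near zero for toxicity limited to the chemotherapy cycles, and vanishes if treatment durations are equal.

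The effect is on interpretation of the safety tables only. The documents do not support a claim that the crude table is wrong or should be replaced: an exposure-adjusted rate used alone would mislead in the opposite direction for early chemotherapy toxicity.

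**What to change.** Keep the crude Tier 2 table. In sSAP 3.5.2, change the exposure-adjusted provision from *may* to *will* for all Tier 2 events, and add the same commitment to protocol 8.6.2. Report two descriptive companions side by side:

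- **(a)** The first-event rate per 100 person-months in each arm, with person-time counted to the first event or the end of the applicable AE or SAE window, Initial Treatment Phase only, and a 95% CI for the rate difference.
- **(b)** An early-period comparison over a fixed calendar window from first dose, for example Days 1 to 84, using time-to-first-event cumulative incidence so that subjects whose window closes early are handled. A calendar window is preferable to the end of Cycle 4, because cycles can be delayed.

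Summarise AEOSIs the same way, without significance tests, which respects the plan's reason for having no Tier 1 events.

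The cost is SAP wording and a few extra tables from data already collected; conduct, sample size and alpha do not change. The one risk is that (a) is read alone for early chemotherapy toxicity, so the text should require (a) and (b) to be shown together.

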### 8.6.3 Summaries of Baseline Characteristics and Demographics

The comparability of the treatment groups for each relevant characteristic will be assessed by the use of tables and/or graphs. No statistical hypothesis tests will be performed on these characteristics. The number and percentage of subjects randomized, and the primary reason for discontinuation will be displayed. Demographic variables (such as age) and baseline characteristics will be summarized by treatment either by descriptive statistics or categorical tables. The reasons for exclusion from the ITT population (if any) will be summarized.

### 8.7 Interim Analyses

Two interim efficacy analyses are planned for this study.

[figure not shown]
- The (IA1) will be performed approximately 18 months from study start. PFS and OS will be evaluated at IA1. ORR p-value from IA1 may be evaluated for statistical significance if PFS and OS null hypotheses are rejected at IA1 or at a later analysis time.
- The second interim analysis (IA2) is the final formal analysis of PFS. It will be performed at approximately 22 months after first subject enrolled. The second interim analysis evaluation of OS will be performed at this time.
- The final analysis will evaluate OS only. It is planned when a minimum of 294 deaths have been observed or approximately 31 months after first subject enrolled, whichever occurs later.

In addition to the formal efficacy analyses, the DMC will conduct regular safety monitoring, the timing of which is specified in the DMC charter. Decisions to stop the trial early will be based on DMC recommendations with review by the EOC.

Type I error control for the efficacy analyses as well as efficacy bounds are described in the next section.

### 8.8 Multiplicity

The trial uses the graphical method of Maurer and Bretz [114] to control multiplicity for multiple hypotheses as well as interim analyses. [Figure 3](#) shows the initial one-sided  $\alpha$  allocation for each hypothesis in the ellipse representing the hypothesis. The weights for reallocation from each hypothesis to the others are represented in the boxes on the lines connecting hypotheses.

Note: If both PFS and OS null hypotheses are rejected, the reallocation strategy allows testing of ORR at  $\alpha=0.025$ .

Figure 3 Multiplicity Graph for Type I Error Control

### Progression-free Survival

If the null hypothesis for OS is rejected, [Figure 3](#) shows that its  $\alpha=0.019$  is essentially fully reallocated to PFS hypothesis testing. Thus, the PFS null hypothesis may be tested at  $\alpha=0.006$  or at  $\alpha=0.025$ . For PFS hypotheses, the targeted number of events at the final PFS analysis will be 387. A Lan-DeMets O'Brien-Fleming spending function will be used for information fraction-based alpha-spending to generate the group sequential design. The bounds provided in [Table 15](#) are based on the assumption that the number of events at IA1 and IA2 are 332 and 387, respectively. The actual boundaries and the nominal alpha level will be determined based on the actual number of PFS events observed at the time of the analyses and from the overall alpha level after any potential alpha-shifting as the result of a successful OS analysis. The final PFS analysis at IA2 will use the remaining Type I error not spent at the IA1, regardless of the actual number of PFS events observed. The p-value bound at the final PFS analysis will be calculated by considering the correlation between the test statistics as determined by the actual number of PFS events at IA1 and the final PFS analysis at IA2. The bounds given in [Table 15](#) will be adjusted accordingly.

Table 15 Efficacy Boundaries and Properties for Progression-free Survival Analyses

Analysis	Targeted Analysis Time	Cumulative alpha spent 	Efficacy Bars 
IA1 (86%  )	Approximately 18 months from study start 	0.003	
 
• (One-sided) p-value <0.003
 
• Observed HR <~ 0.74
 

IA2 (100%  )	Approximately 22 months from study start 	0.006	
 
• (One-sided) p-value <0.0051
 
• Observed HR <~ 0.77
 

 Nominal alpha, boundaries, and cumulative alpha are based on the assumption that 332 and 387 events are at IA1 and IA2, respectively. The p-value boundaries will be updated at the time of analyses based on actual number of PFS events.

 Percentage of expected number of events at final analysis targeted at interim analysis.

 Study start is defined as the date when the first subject was randomized.

Note that if the  $\alpha$ -reallocation from OS hypothesis testing occurs at the final analysis after hypothesis testing for PFS has been completed, the previously computed PFS test statistic for the PFS final analysis may be re-evaluated based on the updated bounds.

### Overall Survival

The OS hypothesis may be tested at  $\alpha=0.019$  (initially allocated  $\alpha$ ) or at  $\alpha=0.025$  (if PFS null hypothesis is rejected) following the multiplicity strategy as outlined in Figure 3. The bounds and boundary properties for OS hypothesis testing at the initial alpha level are demonstrated in Table 16. The alpha spending at each interim analysis is determined using a Lan-DeMets O'Brien-Fleming spending function, and the information fraction (ratio of the actual number of events at the interim analysis relative to a targeted 294 events at the final analysis). The final analysis will use the remaining Type I error not spent at earlier analyses, regardless of the number of events observed at the final analysis. The p-value bounds at second interim and final analysis will be calculated by considering the correlation between the test statistics as determined by the actual number of OS events at the previous and current analysis. The p-value bounds at each analysis time may also be updated after potential alpha-shifting as the result of a successful PFS analysis.

Table 16 Efficacy Boundaries and Properties for Overall Survival Analyses

Analysis	Targeted Analysis Time	Cumulative alpha spent 	Efficacy Bars 
IA1 (60%  )	Approximately 18 months from study start 	0.0024	
 
• (One-sided) p-value <0.0024
 
• Observed HR <~ 0.65
 

IA2 (76%  )	Approximately 22 months from study start 	0.0071	
 
• (One-sided) p-value <0.0064
 
• Observed HR <~ 0.72
 

FA (100%  )	A minimum of 294 deaths observed in 2 arms or approximately 31 months from study start, whichever occurs later 	0.019	
 
• (One-sided) p-value <0.0167
 
• Observed HR <~ 0.78
 

 Nominal alpha, boundaries, and cumulative alpha are based on the number of deaths expected assuming the projected number of events using protocol assumptions, ie, 175, 224, and 294 at IA1, IA2 and final analysis, respectively. The p-value boundaries will be updated at the time of analyses based on actual number of deaths.

 Percentage of expected number of events at final analysis targeted at interim analysis.

 Study start is defined as the date when the first subject was randomized.

The DMC has responsibility for assessment of overall risk: benefit. When prompted by safety concerns, the DMC can request corresponding efficacy data. DMC review of efficacy data to assess the overall risk: benefit to study participants will not require a multiplicity adjustment typically associated with a planned efficacy IA. However, to account for any multiplicity concerns raised by the DMC review of unplanned efficacy data when prompted by safety concerns, a sensitivity analysis for OS adopting a conservative multiplicity adjustment will be pre-specified in the sSAP.

